7.2.4 Visit #4. Bronchoscopy #2 / Treatment Session #2

Subjects are scheduled for follow-up 3-6 weeks following Bronchoscopy #1. Pre-operative procedures (e.g. CT Scan, physical exam, CBC) are completed in accordance with the Schedule of Events table prior to the bronchoscopy. Any observed adverse events are reported accordingly. If the subject has experienced any complications that preclude continued participation in the study, then additional treatment is halted.

Upon successful completion of the pre-operative procedures, the subject undergoes a bronchoscopy procedure in accordance with standard institutional protocol. Anesthesia is administered. The airways are visualized, and BAL completed. The RheOx Bronchial Rheoplasty is administered to the target sites in the left side lung in accordance with the instructions for use. The clinical investigator ensures FiO₂ does not exceed 40% during energy delivery. Prior to the initiation of energy delivery and during at least one energy delivery a 6 second 3 lead EKG strip is recorded. An EKG rhythm strip from anesthesia monitoring is adequate.

The subject is recovered in accordance with standard institutional procedures and observed overnight at the discretion of the study investigator. The subject is then discharged at the investigator's discretion. Any observed adverse events are reported accordingly.

Note: Bronchoscopy #2 may be delayed or halted at the investigator's discretion if the patient has an active respiratory infection (e.g., common cold, pneumonia, MAI), COPD exacerbation since treatment session #1 or any other significant clinical symptom that may compromise the procedure.

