3 STUDY OVERVIEW

3.1 Study Design

This is a prospective, single arm, feasibility study to assess the safety and clinical utility of RheOx in patients with chronic bronchitis in the United States.

Patients undergo the RheOx Bronchial Rheoplasty procedure in two bronchoscopic sessions; the first to treat the right lung (Bronchoscopy 1 / index procedure) and the second to treat the left lung (Bronchoscopy 2) approximately 4-weeks later. Study follow-up visits occur at 1-week following each treatment and at 1-month, 3-months, 6-months, 10-months, 12-months, and 2, 3, 4 and 5 years after the second treatment.

For a detailed schedule of procedures, refer to the Schedule of Events table in the study protocol.

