4.8.1 Serious Adverse Events of Interest

The primary safety analysis is the incidence of treatment emergent serious adverse events of interest through 12 months. Serious adverse events of interest are defined in the study protocol and in Section 3.2.1 above.

The count and percent of patients experiencing each of the events listed in Section 3.2.1 above and a composite summary of patients experiencing any of these events through the 12-month visit will be summarized. Events will also be summarized within discrete time periods (as described in section below) from bronchoscopy #1 (Visit #2) through 12 months in order to assess the procedure effect.

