4.8.2 Adverse Events

All reported AEs will be coded and classified by system organ class and lower level term (LLT) using the Medical Dictionary for Regulatory Activities (MedDRA).

The relationship to the device and/or procedure, system organ class, lower level term (LLT), and verbatim text for all adverse events will be listed. All treatment emergent AEs and SAEs will be summarized by the system organ class, LLT, and time interval. Device and/or procedure related adverse events will be summarized in a similar manner.

The following time intervals will be used:

- Treatment Emergent: Any event that occurred the day of or following Bronchial Rheoplasty 1 procedure through end of study.
- Treatment Recovery Period: Any event occurring the day of Bronchial Rheoplasty 1 procedure through 30 days following Bronchial Rheoplasty 2 procedure.
- 3 Months: Any event occurring during follow-up period through 90 days after Bronchial Rheoplasty 2, excluding treatment recovery period.

CONFIDENTIAL:

This document and its contents are the property of Gala Therapeutics, Inc. Any use, reproduction or distribution without the written permission of Gala Therapeutics, Inc. is prohibited.

	TYPE: Clinical Trial Document	Document No:	CLN-0000X
	TITLE: CS003 Statistical Analysis Plan	Revision:	A
		Release Date:	
		DCN	Page 9 of 44

- 6 Months: Any event occurring during the follow-up period between 91 days and 180 days after Bronchial Rheoplasty 2.
- 12 Months: Any event occurring during the follow-up period between 181 days and 365 days after Bronchial Rheoplasty 2.
- 2 Years: Any event occurring during the follow-up period between 366 days after Bronchial Rheoplasty 2 and 730 days after Bronchial Rheoplasty 2.
- 3 Years: Any event occurring during the follow-up period between 731 days and 1095 days after Bronchial Rheoplasty 2.
- 4 Years: Any event occurring during the follow-up period between 1096 days and 1460 days after Bronchial Rheoplasty 2.
- 5 Years: Any event occurring during the follow-up period between 1461 days and study completion.

SAEs and/or AEs leading to the discontinuation of study will also be listed.

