Patient Meeting Criteria #3 n (%)	xx (xx.x%)	xx (xx.x%)	xx (xx.x%)	xx (xx.x%)	xx (xx.x%)	xx (xx.x%)	xx (xx.x%)
Patient Meeting Criteria #4 n (%)	xx (xx.x%)	xx (xx.x%)	xx (xx.x%)	xx (xx.x%)	xx (xx.x%)	xx (xx.x%)	xx (xx.x%)

CONFIDENTIAL:

This document and its contents are the property of Gala Therapeutics, Inc. Any use, reproduction or distribution without the written permission of Gala Therapeutics, Inc. is prohibited

	TYPE: Clinical Trial Document	Document No:	CLN-0000X
	TITLE: CS003 Statistical Analysis Plan	Revision:	A
		Release Date:	
		DCN	Page 32 of 44

Table # 14.3.1 Serious Adverse Events of Interest and Hospitalizations
Evaluable Population

	Treatment Recovery Period [1]	3 Months [2]	6 Months [3]	12 Months [4]	Total Events through 12 Months [5]
	n (%) [events]	n (%) [events]	n (%) [events]	n (%) [events]	n (%) [events]
	(N)	(N)	(N)	(N)	(N)
Death	xx (xx.x%) [xx]	xx (xx.x%) [xx]	xx (xx.x%) [xx]	xx (xx.x%) [xx]	xx (xx.x%) [xx]
COPD Exacerbation	xx (xx.x%) [xx]	xx (xx.x%) [xx]	xx (xx.x%) [xx]	xx (xx.x%) [xx]	xx (xx.x%) [xx]
Pneumothorax	xx (xx.x%) [xx]	xx (xx.x%) [xx]	xx (xx.x%) [xx]	xx (xx.x%) [xx]	xx (xx.x%) [xx]
Pneumonia	xx (xx.x%) [xx]	xx (xx.x%) [xx]	xx (xx.x%) [xx]	xx (xx.x%) [xx]	xx (xx.x%) [xx]
Respiratory Failure	xx (xx.x%) [xx]	xx (xx.x%) [xx]	xx (xx.x%) [xx]	xx (xx.x%) [xx]	xx (xx.x%) [xx]
Arrythmia	xx (xx.x%) [xx]	xx (xx.x%) [xx]	xx (xx.x%) [xx]	xx (xx.x%) [xx]	xx (xx.x%) [xx]
Total					
Hospitalizations					
n (%)	xx (xx.x%)	xx (xx.x%)	xx (xx.x%)	xx (xx.x%)	xx (xx.x%)
Rate per pt-yr (n events)	x.xx [xx]	x.xx [xx]	x.xx [xx]	x.xx [xx]	x.xx [xx]

[1] Any event occurring after Bronchial Rheoplasty 1 procedure through 30 days following Bronchial Rheoplasty 2 procedure.

[2] Follow-up period through 3 months after Bronchial Rheoplasty 2, excluding either treatment recovery period.

[3] Follow-up period between 3 months and 6 months after Bronchial Rheoplasty 2.

[4] Follow-up period between 6 months and 12 months after Bronchial Rheoplasty 2.

[5] All treatment-emergent events occurring after Bronchial Rheoplasty 1 procedure through 12 months after Bronchial Rheoplasty 2.

CONFIDENTIAL:

	TYPE: Clinical Trial Document	Document No:	CLN-0000X
	TITLE: CS003 Statistical Analysis Plan	Revision:	A
		Release Date:	
		DCN	Page 33 of 44

Table # 14.3.2 High Level Summary of Non-Serious Adverse Events
Evaluable Population

	Total Events through 12 Months[1] n (%) [events] (N)
Number of Subjects with AEs	xx (x.x%) [xx]

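### Interval columns for the SAEs of interest and the AE/SAE totals carry no patient-time, so the 185-day 12 Months column cannot be compared directly with the 52-73 day recovery column

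*SAP*

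**What the plan says.** SAP 4.8.1 makes the 12-month count and percent of patients with SAEs of interest the primary safety summary, by event and as a composite. It then adds a summary within time periods running "from bronchoscopy #1 (Visit #2) through 12 months in order to assess the procedure effect". SAP 4.8.2 defines the periods:

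- The recovery column takes in "Any event occurring the day of Bronchial Rheoplasty 1 procedure through 30 days following Bronchial Rheoplasty 2 procedure".
- Next comes the column headed 3 Months, which is defined as "Any event occurring during follow-up period through 90 days after Bronchial Rheoplasty 2, excluding treatment recovery period".
- The column after that, 6 Months, holds whatever falls "between 91 days and 180 days after Bronchial Rheoplasty 2".
- The last of the four, labelled 12 Months, covers "Any event occurring during the follow-up period between 181 days and 365 days after Bronchial Rheoplasty 2".

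In Table 14.3.1 the six event rows give n (%) and the event count in each period column, with no patient-time and no rate. Tables 14.3.4 (non-serious AEs) and 14.3.6 (SAEs) have the same layout. Two displays do adjust for time over the same periods. The Hospitalizations block of Table 14.3.1 has a line beginning "Rate per pt-yr (n events", and Table 14.3.8 gives COPD exacerbation rates per patient-year, including a severe row. SAP 4.8 rules out inferential testing of the safety data.

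**The concern.** The period split exists to show whether events cluster around the procedures. That comparison needs columns on a common time scale. A count or percentage accumulates with the length of the window, and the last window is about three times as long as the recovery window. With no procedure effect at all, the percentages rise from left to right after recovery simply because the windows get longer. The longest and latest column is the natural one to read as background, and it is the least comparable with recovery. Since no safety testing is planned, these descriptive columns are all the report will offer on timing for the affected rows.

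**Working it through.** The documents give no rate, hazard ratio or power figure to reproduce. The check uses the window lengths.

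**Inputs**
- Gap between procedures: Protocol 7.2.4, "Subjects are scheduled for follow-up 3-6 weeks following Bronchoscopy #1", so 21 to 42 days. The nominal gap in SAP 3.1 is 28 days: "the second to treat the left lung (Bronchoscopy 2) approximately 4-weeks later".
- Period limits: SAP 4.8.2, as quoted above.
- Sample size: up to 30 (SAP 4.1).
- Background rate: not given in the documents. Assumed 0.1 to 1.0 per patient-year, with 0.3 as the worked example.

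**Window lengths, counted inclusively**
- Recovery = gap + 31: 21 + 31 = 52, 28 + 31 = 59, 42 + 31 = 73 days.
- 3 Months: 90 - 31 + 1 = 60 days.
- 6 Months: 180 - 91 + 1 = 90 days.
- 12 Months: 365 - 181 + 1 = 185 days.

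**Break-even hazard ratio.** This is the recovery-period hazard ratio at which the recovery column only equals the comparison column. It is the comparison length divided by the recovery length, and it does not depend on the background rate.

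| Recovery against | 52 days | 59 days | 73 days |
|---|---|---|---|
| 3 Months (60) | 1.15 | 1.02 | 0.82 |
| 6 Months (90) | 1.73 | 1.53 | 1.23 |
| 12 Months (185) | 3.56 | 3.14 | 2.53 |

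The same ratios give the expected events in each later column relative to recovery when the hazard is constant. At the 28-day gap the total is 59 + 60 + 90 + 185 = 394 days, so window length alone puts about 15%, 15%, 23% and 47% of the events in the four columns.

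**Worked example.** Expected percent of patients with an event = 1 - exp(-rate x HR x days / 365.25). With a rate of 0.3, HR 3 in recovery only, and a 28-day gap:
- Recovery: 1 - exp(-0.3 x 3 x 59 / 365.25) = 13.5%, about 4.1 of 30 patients.
- 3 Months: 4.8%, about 1.4 patients.
- 6 Months: 7.1%, about 2.1 patients.
- 12 Months: 14.1%, about 4.2 patients.

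The tripled hazard disappears against 12 Months, but it is nearly 3 times the 3 Months figure and nearly twice the 6 Months figure. The order of recovery and 12 Months is the same at other assumed rates: 4.7% against 4.9% at 0.1, and 38.4% against 39.7% at 1.0. At a 42-day gap the tripled hazard does show against 12 Months (16.5% against 14.1% at a rate of 0.3), as the break-even of 2.53 implies.

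**With rates instead.** In the same example the patient-years are 30 x 59 / 365.25 = 4.85 in recovery and 30 x 185 / 365.25 = 15.20 in 12 Months. Expected events are 4.85 x 0.9 = 4.4 and 15.20 x 0.3 = 4.6. The displayed rates would be 0.9 and 0.3 per patient-year, a ratio of 3.

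**Rows affected.** By the definitions in SAP 3.2.1, pneumothorax counts only within 2 days and pneumonia only within 7 days of a procedure. Both can fall only in the recovery column and cannot be masked. The effect reaches death, respiratory failure, arrhythmia and the >24-hour exacerbation row. It reaches the composite through those four, and it also reaches the AE and SAE totals.

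**The case against.** The strongest reply is that the plan already has several views of the procedure effect. The 3 Months column is almost as long as recovery, so an attentive reader has a fair comparator in the same table. Table 14.3.8 gives exacerbation rates for the same windows and for the 12 months before treatment. Table 14.3.1 gives hospitalization rates. Tables 14.3.4 and 14.3.6 split events by device and procedure relatedness, which does not depend on window length. The primary 12-month incidence is untouched, the period split is supplementary, and 30 patients will produce few events.

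Most of this stands, and it limits the point. It does not remove it. Relatedness rests on investigator judgement in an unblinded study. The severe exacerbations of Table 14.3.8 are defined more broadly than the SAE of interest, because the Protocol's definition includes emergency room visits while the SAE needs a stay of more than 24 hours. Death, respiratory failure, arrhythmia and the composite have no time-adjusted figure anywhere.

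A reader might infer more than the documents support:

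- **That the split cannot serve its purpose, or always favours the device.** The direction depends on the column chosen. Against 3 Months with a 6-week gap, the layout tilts slightly towards showing an excess (break-even 0.82), and a delayed second procedure, which Protocol 7.2.4 allows, lengthens recovery further.
- **That the yearly Tables 14.3.5 and 14.3.7 have the same fault.** Their 2, 3 and 4 Years windows are each 365 days; only the last is open-ended.
- **That pooling both procedures in one recovery column is an error.** SAP 4.8.1 speaks of a procedure effect and promises no comparison of the first treatment with the second.

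**Conclusion.** The point holds, limited to the affected rows and mainly to the comparison with 12 Months. There the unequal windows alone produce a 2.5- to 3.6-fold difference at constant hazard, enough to hide a recovery-period hazard of up to about 3 times background. The comparison with 3 Months is close to fair, and that with 6 Months is off by a factor of about 1.2 to 1.7. These factors rest on the SAP's day limits, a 3 to 6 week gap, full observation in each window and a constant background hazard. Only the example percentages depend on the assumed rates. The SAP already uses patient-year rates over the same windows elsewhere and gives no reason for leaving them out here. This is a correctable weakness in a supporting display and does not affect the validity of the primary 12-month result.

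**What to change.** In Tables 14.3.1, 14.3.4 and 14.3.6, show the patient-years under observation in each interval. Add events per patient-year for death, respiratory failure, arrhythmia, the >24-hour COPD exacerbation, the composite and the AE/SAE totals, with exact Poisson intervals if wanted. Add a sentence to SAP 4.8.1 saying that comparisons between periods are read from the rates. Keep the existing n (%) and event counts, including the primary 12-month figure.

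The cost is small: a change to the SAP text and table shells, plus some programming. Interval patient-time is already needed for the hospitalization and exacerbation rates. The drawbacks are wider tables and rates that will be imprecise with at most 30 patients, although showing the patient-years makes that imprecision visible. Splitting the recovery column at the second procedure is optional. Tables 14.3.5 and 14.3.7 need no change.

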4.8.2 Adverse Events

All reported AEs will be coded and classified by system organ class and lower level term (LLT) using the Medical Dictionary for Regulatory Activities (MedDRA).

The relationship to the device and/or procedure, system organ class, lower level term (LLT), and verbatim text for all adverse events will be listed. All treatment emergent AEs and SAEs will be summarized by the system organ class, LLT, and time interval. Device and/or procedure related adverse events will be summarized in a similar manner.

The following time intervals will be used:

- Treatment Emergent: Any event that occurred the day of or following Bronchial Rheoplasty 1 procedure through end of study.
- Treatment Recovery Period: Any event occurring the day of Bronchial Rheoplasty 1 procedure through 30 days following Bronchial Rheoplasty 2 procedure.
- 3 Months: Any event occurring during follow-up period through 90 days after Bronchial Rheoplasty 2, excluding treatment recovery period.

CONFIDENTIAL:

This document and its contents are the property of Gala Therapeutics, Inc. Any use, reproduction or distribution without the written permission of Gala Therapeutics, Inc. is prohibited.

	TYPE: Clinical Trial Document	Document No:	CLN-0000X
	TITLE: CS003 Statistical Analysis Plan	Revision:	A
		Release Date:	
		DCN	Page 9 of 44

- 6 Months: Any event occurring during the follow-up period between 91 days and 180 days after Bronchial Rheoplasty 2.
- 12 Months: Any event occurring during the follow-up period between 181 days and 365 days after Bronchial Rheoplasty 2.
- 2 Years: Any event occurring during the follow-up period between 366 days after Bronchial Rheoplasty 2 and 730 days after Bronchial Rheoplasty 2.
- 3 Years: Any event occurring during the follow-up period between 731 days and 1095 days after Bronchial Rheoplasty 2.
- 4 Years: Any event occurring during the follow-up period between 1096 days and 1460 days after Bronchial Rheoplasty 2.
- 5 Years: Any event occurring during the follow-up period between 1461 days and study completion.

SAEs and/or AEs leading to the discontinuation of study will also be listed.

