3.2.3 Other Endpoints

Other, tertiary and exploratory endpoints will also be assessed including changes from baseline to follow-up in;

- Responder rates utilizing established clinically meaningful thresholds for SGRQ (4 points)¹⁷ and CAT (2 points)¹⁶
- Change in other QOL measures including CASA-Q and EXACT-PRO
- Change in lung function as measured by FEV₁ and FVC
- Change in sleep patterns as assessed by the Insomnia Sleep Index (ISI)
- Change in cough count as assessed by a cough counting monitor
- Mucin concentrations (MUC5AC, MUC5B) from induced sputum samples
- Quantitative High Resolution CT Scan (HRCT) metrics including airway volume, total airway count, and lobar volumes
- Device performance

In addition to the endpoints described above, additional safety analyses in support of the primary study outcome and to assess the totality of safety profile of the RheOx Bronchial Rheoplasty, will be conducted.

Adverse events reported from the day of the index procedure through completion or termination of the study will be assessed. AEs and SAEs will be summarized using a standard medical coding dictionary (MedDRA). AEs and SAEs will be also analyzed by severity, relatedness to the device and/or procedure and within discrete time periods relative to the index procedure.

COPD exacerbations will also be analyzed by severity (mild, moderate, and severe) based on commonly accepted clinical definitions as defined in GOLD 2018 Report¹⁸.

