Number of Subjects with Related AEs	xx (x.x%) [xx]
Number Subjects Withdrawn Due to an AE	xx (x.x%) [xx]
AE Severity	xx (x.x%) [xx]
Mild	xx (x.x%) [xx]
Moderate	xx (x.x%) [xx]
Severe	xx (x.x%) [xx]
AE Relationship to Procedure	xx (x.x%) [xx]
Probably Related	xx (x.x%) [xx]
Possibly Related	xx (x.x%) [xx]
Not Related	xx (x.x%) [xx]
AE Relationship to Device	xx (x.x%) [xx]
Probably Related	xx (x.x%) [xx]
Possibly Related	xx (x.x%) [xx]
Not Related	xx (x.x%) [xx]
AE Outcome	xx (x.x%) [xx]
Resolved	xx (x.x%) [xx]
Resolved with sequelae	xx (x.x%) [xx]
Ongoing	xx (x.x%) [xx]
Death	xx (x.x%) [xx]

[1] All treatment-emergent events occurring after Bronchial Rheoplasty 1 procedure through 12 months after Bronchial Rheoplasty 2.

CONFIDENTIAL:

This document and its contents are the property of Gala Therapeutics, Inc. Any use, reproduction or distribution without the written permission of Gala Therapeutics, Inc. is prohibited

	TYPE: Clinical Trial Document	Document No:	CLN-0000X
	TITLE: CS003 Statistical Analysis Plan	Revision:	A
		Release Date:	
		DCN	Page 34 of 44

Table # 14.3.3 High Level Summary of Serious Adverse Events
Evaluable Population

	Total Events through 12 Months [1] n (%) [events] (N)
Number of Subjects with SAEs	xx (x.x%) [xx]
Number of Subjects with Related SAEs	xx (x.x%) [xx]
Number Subjects Withdrawn Due to an SAE	xx (x.x%) [xx]
SAE Severity	xx (x.x%) [xx]
Mild	xx (x.x%) [xx]
Moderate	xx (x.x%) [xx]
Severe	xx (x.x%) [xx]
SAE Relationship to Procedure	xx (x.x%) [xx]
Probably Related	xx (x.x%) [xx]
Possibly Related	xx (x.x%) [xx]
Not Related	xx (x.x%) [xx]
SAE Relationship to Device	xx (x.x%) [xx]
Probably Related	xx (x.x%) [xx]
Possibly Related	xx (x.x%) [xx]
Not Related	xx (x.x%) [xx]
SAE Outcome	xx (x.x%) [xx]
Resolved	xx (x.x%) [xx]
Resolved with sequelae	xx (x.x%) [xx]
Ongoing	xx (x.x%) [xx]
Death	xx (x.x%) [xx]

[1] All treatment-emergent events occurring after Bronchial Rheoplasty 1 procedure through 12 months after Bronchial Rheoplasty 2.

CONFIDENTIAL:

This document and its contents are the property of Gala Therapeutics, Inc. Any use, reproduction or distribution without the written permission of Gala Therapeutics, Inc. is prohibited

	TYPE: Clinical Trial Document	Document No:	CLN-0000X
	TITLE: CS003 Statistical Analysis Plan	Revision:	A
		Release Date:	
		DCN	Page 35 of 44

Table # 14.3.4 Non-Serious Adverse Event Summary through 12 Months

Evaluable Population

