Relationship/ Adverse Event	Treatment Recovery Period		3 Months		6 Months		12 Months		Total Events through 12 Months	
	n (%) [event] [1] (N)		n (%) [event] [2] (N)		n (%) [event] [3] (N)		n (%) [event] [4] (N)		n (%) [event] [5] (N)	
Number of TEAEs	xx		xx		xx		xx		xx	
Number of Subjects with any TEAEs	xx (xx.x%) [xx]	xx	xx (xx.x%) [xx]	xx	xx (xx.x%) [xx]	xx	xx (xx.x%) [xx]	xx	xx (xx.x%) [xx]	xx
Number of Subjects	xx		xx		xx		xx		xx	
All Adverse Events	xx (xx.x%) [xx]	xx	xx (xx.x%) [xx]	xx	xx (xx.x%) [xx]	xx	xx (xx.x%) [xx]	xx	xx (xx.x%) [xx]	xx
SOC	xx (xx.x%) [xx]	xx	xx (xx.x%) [xx]	xx	xx (xx.x%) [xx]	xx	xx (xx.x%) [xx]	xx	xx (xx.x%) [xx]	xx
LLT	xx (xx.x%) [xx]	xx	xx (xx.x%) [xx]	xx	xx (xx.x%) [xx]	xx	xx (xx.x%) [xx]	xx	xx (xx.x%) [xx]	xx
LLT	xx (xx.x%) [xx]	xx	xx (xx.x%) [xx]	xx	xx (xx.x%) [xx]	xx	xx (xx.x%) [xx]	xx	xx (xx.x%) [xx]	xx
Device-Related Only [6]	xx (xx.x%) [xx]	xx	xx (xx.x%) [xx]	xx	xx (xx.x%) [xx]	xx	xx (xx.x%) [xx]	xx	xx (xx.x%) [xx]	xx
SOC										
LLT										
LLT										
Procedure-Related Only [6]										
SOC										
LLT										
LLT										
Device-Related and Procedure-Related [6]										
SOC										
LLT										
LLT										

[1] Any event occurring after Bronchial Rheoplasty 1 procedure through 30 days following Bronchial Rheoplasty 2 procedure.

[2] Follow-up period through 3 months after Bronchial Rheoplasty 2, excluding either treatment recovery period.

[3] Follow-up period between 3 months and 6 months after Bronchial Rheoplasty 2.

[4] Follow-up period between 6 months and 12 months after Bronchial Rheoplasty 2.

[5] All treatment-emergent events occurring after Bronchial Rheoplasty 1 procedure through 12 months after Bronchial Rheoplasty 2.

[6] Events are considered device-related or procedure-related if judged by the treating investigator to be possibly, probably or definitely related to the device or procedure, respectively.

CONFIDENTIAL:

	TYPE: Clinical Trial Document	Document No:	CLN-0000X
	TITLE: CS003 Statistical Analysis Plan	Revision:	A
		Release Date:	
	DCN	Page 36 of 44	

Table # 14.3.5 Non-Serious Adverse Event Summary Post 12 Months

Evaluable Population

Relationship/ Adverse Event	2 Years [1]		3 Years [2]		4 Years [3]		5 Years [4]		Post-12 Months Total [5]	
	n (%)	[events] N	n (%)	[events] N	n (%)	[events] N	n (%)	[events] N	n (%)	[events] N
Number of TEAEs	xx		xx		xx		xx		xx	
Number of Subjects with any TEAEs	xx (xx.x%)	[xx]	xx (xx.x%)	[xx]	xx (xx.x%)	[xx]	xx (xx.x%)	[xx]	xx (xx.x%)	[xx]

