[6] Events are considered device-related or procedure-related if judged by the treating investigator to be possibly, probably or definitely related to the device or procedure, respectively.

CONFIDENTIAL:

This document and its contents are the property of Gala Therapeutics, Inc. Any use, reproduction or distribution without the written permission of Gala Therapeutics, Inc. is prohibited

	TYPE: Clinical Trial Document	Document No:	CLN-0000X
	TITLE: CS003 Statistical Analysis Plan	Revision:	A
		Release Date:	
		DCN	Page 39 of 44

Table # 14.3.8 COPD Exacerbation Rates
Evaluable Population

COPD Exacerbation (LLT) Event Rate per Patient-Year +/- SD [events]	Baseline (12 Months prior to Treatment) (N)	Post-Treatment Total (12 Months Post Treatment) [1] (N)	Post-Treatment Total, Excluding Treatment Recovery Period [2] (N)	Treatment Recovery Period [3] (N)	3 Months [4] (N)	6 Months [5] (N)	12 Months [6] (N)
All	x.xx +/- x.xx [xx]	x.xx +/- x.xx [xx]	x.xx +/- x.xx [xx]	x.xx +/- x.xx [xx]	x.xx +/- x.xx [xx]	x.xx +/- x.xx [xx]	x.xx +/- x.xx [xx]
Moderate	x.xx +/- x.xx [xx]	x.xx +/- x.xx [xx]	x.xx +/- x.xx [xx]	x.xx +/- x.xx [xx]	x.xx +/- x.xx [xx]	x.xx +/- x.xx [xx]	x.xx +/- x.xx [xx]
Severe	x.xx +/- x.xx [xx]	x.xx +/- x.xx [xx]	x.xx +/- x.xx [xx]	x.xx +/- x.xx [xx]	x.xx +/- x.xx [xx]	x.xx +/- x.xx [xx]	x.xx +/- x.xx [xx]

[1] All treatment-emergent events occurring after Bronchial Rheoplasty 1 procedure through 12 months after Bronchial Rheoplasty 2.

[2] All treatment-emergent events occurring after Bronchial Rheoplasty 1 procedure through 12 months after Bronchial Rheoplasty 2, excluding treatment recovery period.

[3] Any event occurring after Bronchial Rheoplasty 1 procedure through 30 days following Bronchial Rheoplasty 2 procedure.

[4] Follow-up period through 3 months after Bronchial Rheoplasty 2, excluding either treatment recovery period.

[5] Follow-up period between 3 months and 6 months after Bronchial Rheoplasty 2.

[6] Follow-up period between 6 months and 12 months after Bronchial Rheoplasty 2.

CONFIDENTIAL:

This document and its contents are the property of Gala Therapeutics, Inc. Any use, reproduction or distribution without the written permission of Gala Therapeutics, Inc. is prohibited

	TYPE: Clinical Trial Document	Document No:	CLN-0000X
	TITLE: CS003 Statistical Analysis Plan	Revision:	A
		Release Date:	
		DCN	Page 40 of 44

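### Tables 14.3.4–14.3.7 report adverse events by SOC and LLT with no level between, so a medical concept coded to several LLTs never gets its own patient percentage

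*SAP*

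**What the plan says.** SAP 4.8.2 fixes the coding level: "All reported AEs will be coded and classified by system organ class and lower level term (LLT". It fixes the same level for reporting: "All treatment emergent AEs and SAEs will be summarized by the system organ class, LLT, and time interval". Related events follow: "Device and/or procedure related adverse events will be summarized in a similar manner". The shells for Tables 14.3.4 to 14.3.7 carry an any-event patient row ("Number of Subjects with any TEAEs" or its serious-event counterpart), then SOC rows with LLT rows beneath them.

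The protocol asks only for the dictionary and names no level: "AEs and SAEs will be summarized using a standard medical coding dictionary (MedDRA" (section 3.2.3). Neither document mentions a preferred term or any grouping of terms, or says why LLT was chosen.

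The primary safety analysis is built differently. SAP 4.8.1 asks for "The count and percent of patients experiencing each of the events listed in Section 3.2.1 above and a composite summary" of patients with any of them, and those events are defined clinically in SAP 3.2.1. Table 14.3.8, on exacerbation rates, is headed "COPD Exacerbation (LLT", whereas SAP 4.8.2.1 grades exacerbations by the GOLD clinical definitions.

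**The concern.** SAP 3.2.1 makes the incidence of treatment-emergent AEs and SAEs a pre-specified safety analysis, meant to show the whole safety profile. A reader of those tables wants to know what fraction of patients had a given medical event. In MedDRA the LLT is the level closest to the reporter's wording, and several LLTs can sit under one preferred term. That is general knowledge of the dictionary, not something the documents state. The shell for Table 14.1.3 lists eight sites, so differences in wording are plausible.

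Where wording differs, a table that stops at LLT shows fragments of an event. The SOC row above is too broad to put them back together. A reader scanning for the commonest events could miss one, or think it rarer than it was.

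**Working it through.** The plan gives no figure to reproduce. SAP 4.1 reports no sample size calculation, neither document gives observed event counts, and SAP 4.8 rules out inferential testing of safety data. The check is therefore a reading of the shells plus an illustration with assumed counts.

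**Which shells are affected**

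| Table | Rows | Affected? |
|---|---|---|
| 14.3.1 | Six protocol-defined events, a total, hospitalizations | No |
| 14.3.2, 14.3.3 | Patient totals by severity, relatedness and outcome (for example "Number of Subjects with SAEs") | No |
| 14.3.4–14.3.7 | Any event, SOC, LLT | LLT rows only |
| 14.3.8 | Exacerbation rates, with an LLT label in the header | Unclear; see below |

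LLT rows appear in 4 of the 8 shells, a fifth carries an LLT label, and 3 use no LLT.

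**Size when a concept is split.** Input from the documents: N = 30, the maximum in SAP 4.1. Assumed: 6 patients have the concept, each coded to one LLT. Row percentage = patients in the row / 30, with exact (Clopper-Pearson) 95% limits.

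- One row: 6/30 = 20.0% (7.7 to 38.6).
- Even split over two LLTs: two rows of 3/30 = 10.0% (2.1 to 26.5).
- Even split over three LLTs: three rows of 2/30 = 6.7% (0.8 to 22.1).
- All six under one LLT: no change.

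If each of the six falls at random into one of k equally likely LLTs, averaging the largest row over all k^6 assignments gives 3.9 patients for k = 2, 3.2 for k = 3 and 2.8 for k = 4, against 6 for the concept.

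**Why the rows cannot be added.** Suppose one of the six has two episodes coded to different LLTs, and the rows hold 4 and 3 patients. Their sum is 7, but the number of distinct patients is 4 + 3 − 1 = 6. The table does not show the overlap, so the concept's patient count cannot be recovered from it.

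**Table 14.3.8.** This table sets post-treatment exacerbation rates beside a rate for the 12 months before treatment. In the protocol's Schedule of Events, adverse events are recorded from Visit 2 onward, while exacerbation history is recorded from screening. The baseline count therefore covers a period before AE collection began. The SAP does not say which terms or records feed either column, or whether one rule selects events in both.

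**The case against.** The strongest reply is that nothing of consequence depends on the LLT rows. The primary endpoint is counted per patient for six clinically defined events plus a composite, and no LLT enters that definition. A reader might infer from a safety-primary trial that its primary result is understated. The documents do not support that. Nor are all safety tables by LLT, since Tables 14.3.1 to 14.3.3 have no such rows.

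The loss is also conditional. It arises only for concepts actually coded to more than one LLT. With consistent coding it is zero, and the counts above are assumed. SAP 4.8.2 lists LLT and verbatim text for every event, so with at most 30 patients synonyms can be spotted and regrouped by hand. All of this stands. But SAP section 1 classes analyses designed after database lock as post hoc and exploratory, so the grouping is better specified beforehand.

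A reader might also infer that LLT rows defeat comparison with the expected frequencies in protocol 10.2, and that preferred terms would restore it. That goes too far. Many 10.2 entries are bundles, such as the anesthesia complications, which no single term level reproduces. The low band, below 1 in 100, cannot be checked with 30 patients, because one patient is already 1/30 = 3.3%. A preferred-term row helps only for single-concept entries such as hemoptysis.

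For Table 14.3.8, it is fair to say that the LLT tag may be only a label, since SAP 4.8.2.1 rests on clinical definitions. A reader might infer that post-treatment exacerbations are picked by one LLT, so that those coded to a synonym drop out and the before-and-after comparison tilts toward benefit. The documents state no such selection rule. What they leave open is which rule applies.

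**Conclusion.** The point holds for the LLT rows of Tables 14.3.4 to 14.3.7. They have no level at which a medical concept coded to several LLTs receives one patient percentage, and such a percentage cannot be rebuilt from the rows. The plan conflicts with no protocol requirement, because the protocol specifies only the dictionary. The matter is one of descriptive reporting in a pre-specified supporting analysis, and it is modest.

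Its size is unknown. It ranges from nothing, for a concept under one LLT, to a halving of the row percentage (20% to 10%) under an even split over two LLTs, or a third (6.7%) over three. These figures rest on assumed counts at N = 30 and on the general structure of MedDRA. Table 14.3.8 has a separate gap: its header names a coding level, its section names a clinical definition, and the SAP does not say which one identifies the events.

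**What to change.** In SAP 4.8.2 and Tables 14.3.4 to 14.3.7, summarize by SOC and preferred term and count each patient once per preferred term within each time interval and in the total column. LLT rows may be nested beneath. Keep LLT and verbatim text in Listing 16.2.4.

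Do not substitute preferred term in Table 14.3.8, because a coarser term may not isolate exacerbations. Remove the LLT tag, and state that exacerbations are identified by the protocol's clinical definition, applied alike to the baseline year and to follow-up.

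No new data are needed. The cost is a few lines of SAP text, revised shells and, if LLT rows are kept, slightly longer tables.
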